 - ii. 10% in \leq 40 seconds (\geq 0.25 m/s)
 - b. 6min WT
 - i. 80% at a distance of \geq 50 m (\geq 0.14 m/s)
 - ii. 20% at a distance \geq 80 m (\geq 0.22 m/s);
 - c. TUG
 - i. 80% in \leq 120 seconds
 - ii. 20% in \leq 90 seconds

2. By session 36 (three months of WALK training), participants will have improved their ability to walk faster and longer distances and will be able to perform exoskeletal-assisted walking tests with or without minimal assistance as follows:
 - a. 10m WT - 70% in ≤ 40 seconds (≥ 0.25 m/s)
 - b. 6min WT - 70% at a distance ≥ 80 m (≥ 0.22 m/s)
 - c. TUG - 60% in ≤ 90 seconds.

Secondary Aims are to affect the following by three months of exoskeletal-assisted walking (WALK):

1. To improve bowel function as measured by established survey instruments; and
2. To reduce total body fat mass and percent as measured by DXA.

Exploratory Aims:

1. To improve autonomic/cardiovascular function (vagal tone) measured by high frequency component of the 24-hour holter monitor;
2. In persons with T6 and above, to improve orthostatic hypotension (OH) tolerance measured by a standard OH challenge test from supine to seated;
3. To improve HDL-c, Homeostatic Model of Assessment – Insulin Resistance (HOMA-IR), serum total testosterone and estradiol levels measured by serum and plasma assay kits; and
4. To improve quality of life (QOL) measured by item banks from the SCI-QOL and Patient Reported Outcomes Measurement Information System (PROMIS).

Hypotheses

Primary Hypothesis (are tested pre and post the WALK arm only):

1. By session 36, 70% of the participants compared with 10% at session 12 will be able to perform the 10m WT ≤ 40 seconds (≥ 0.25 m/s);
2. By session 36, 70% of the participants compared with 10% at session 12 will be able to perform the 6min WT distance ≥ 80 m (≥ 0.22 m/s); and
3. By session 36, 60% of the participants compared with 20% at session 12 will be able to perform the TUG in ≤ 90 seconds.

Secondary Hypotheses (are tested between the WALK arm and the UA arm, within-subject)

4. Bowel function will improve by 25% using the Ten-Question bowel survey. (Note, the components of this survey represent a 50% reduction in bowel evacuation (BE) time, a 25% increase in BE weekly frequency per week, a 50% reduction in BE medication use, and/or a 25% improvement in stool consistency from harder to softer.)

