5. Total body fat mass is hypothesized to be reduced on average by 9 ± 7 percent (an average of 1.9 ± 1.2 kg decrease from baseline).

Exploratory Hypotheses:

1. In Group 1 (WALK first), the bowel improvement changes will return to baseline values by one month of the UA arm.
2. In Group 1 (WALK first), the body fat mass and percent changes will return to baseline values by 3 months of the UA arm.
3. Associated with increased activity, there will be improved autonomic/cardiovascular function (vagal tone) as measured by the high frequency component of the holter monitor recordings and the tolerance to orthostatic challenge.
4. Associated with increased activity and fat mass loss, there will be statistically significant improvement in HDL-c, HOMA-IR, serum total testosterone and estradiol levels
5. Quality of life (using select SCI-QOL item banks) will be reported to be improve after in the WALK arm, but not for the UA arm

Safety concerns with the use of the exoskeletal devices will continue to be evaluated. Any serious (SAEs) or adverse events (AEs) will be recorded and reported the appropriate oversight bodies.

Study Design

Research design: A Phase III randomized clinical trial (RCT) will be performed using a crossover design and employing an exoskeletal-assisted walking intervention. The experimental arm will be compared to a usual activities (UA) arm, as the control, in 132 persons with chronic SCI (>6 month post injury) who are wheelchair-dependent for outdoor mobility in the community. Eligible participants will be randomized (within site) to one of two groups for 12 weeks (three months): Group 1 (n=32) will receive exoskeletal-assisted walking (WALK) first for 12 weeks then crossover UA for a second 12 weeks; Group 2 (n=32) will receive UA first for 12 weeks then cross-over to the WALK arm for 12 weeks of training. The WALK arm will consist of supervised exoskeletal-assisted walking training, three sessions per week (4-6 h/week) for 36 sessions for their second 12-week period. The UA arm will consist of identification of usual activities for each participant, encouragement to continue with these activities and attention by study team members throughout the 12-week UA arm. These activities will be recorded in a weekly log. A fixed answer format will be used to capture this information.

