Mobility Skills: Exoskeletal-assisted walking tests for the 10m WT, 6min WT, and TUG will be performed at least one time per week during the WALK arm intervention. It was observed during the Phase II trial that weekly assessment of the walking tests provided structured feedback to the participants regarding their progress in mastering the use of the powered exoskeleton and was useful in motivating the participants. Additional mobility skills (turning, wall rest, stopping, and navigating doors) will be assessed throughout the WALK arm; but not to be considered as part of the primary outcomes. The walking tests will be performed as per the standardized descriptions^{52,53} with modifications for the exoskeletons. The PI and lead biomedical engineer from the JJPVAMC ([name]) have significant experience and expertise in performing these walking and mobility tests and will travel to the other two sites to train the staff for standardization purposes across the sites during the designated start-up time of the study.

Body Composition: A dual energy x-ray absorptiometry (DXA) scan for regional and total body fat, lean and bone tissue masses will be performed three times: at baseline, at crossover, and after the second arm of the study for both the WALK and UA arm interventions. Standardized DXA scans will be performed as previously described at all three study sites^{2,3,54}.

ISNCSCI: A neurological evaluation for sensory and motor function, level of injury and lower extremity motor scores will be performed according to the ISNCSCI standards⁵⁵. This exam will be performed three times: at baseline, at crossover, and after the second leg of the study for both the WALK and UA arm interventions.

Bowel function surveys: The 10Q Bowel Function Survey (BFS) and the Bristol Stool Scale will be administered before both interventions and then bi-weekly (two times/month) for a total of 16 times during the two arms of the study. This information will be used to determine key components to a participant's weekly bowel regime²³. The Bowel Management item bank short form from the SCI-QOL will be performed three times: at baseline, at crossover, and after the second arm for both the WALK and UA arm interventions. The PI will instruct the three sites on the standardized method for administering these assessments.

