Methods for recruiting subjects: Three sites will participate in this study: 1) JJPVAMC will be the Lead Site and has four ReWalk units; 2) UMROI will be a sub award site and has two ReWalk units with the potential to acquire two additional units through collateral funding and 3) KFRC will be a sub site of the JJPVAMC through the satellite Center of the Spinal Cord Damage Research Center which is located at Kessler Institute of Rehabilitation. KFRC has one Ekso unit. The JJPVAMC and KFRC study sites each have close to 3 years of experience conducting studies using the exoskeletal systems for persons with SCI. UMROI has recently acquired two ReWalk units and has experience conducting a DOD CDMRP Clinical Trial in persons with SCI. UMROI has begun to study the ReWalk in their patients. Potential participants will be recruited from the research databases at each institution and from the clinical outpatient services. At the UMROI site, the principal investigator also is the Director of the SCI support team clinic at the Baltimore VA Medical Center, so he will be able to recruit from both a civilian and a veteran population. Currently, both the JJPVAMC and KFRC have a waiting list of participants who have contacted either Center to become involved an exoskeletal-assisted walking program. All three study sites have a positive and significant history of recruiting and conducting ethically appropriate clinical trials in persons with SCI.

Expected withdrawal rates: In 13 participants enrolled to date at the JJPVAMC, three withdrew (one due to job relocation, one due to an unrelated medical illness, and one due to difficulty with travel). It is expected that these and/or similar reasons will affect the compliance and attendance of this study to some degree. As such a total of 132 participants will be enrolled as follows: JJPVAMC (n=28, T3 and below), KFRC (n=16, T2 and above) and UMROI (n=20, T3 and below). An enrollment schedule by site is provided (**Table 4**).

Table 4. Original Enrollment Schedule by Site

Study Sites and Groups		Y1				Y2				Y3				Y4				Sub Total
		Q1	Q2	Q3	Q4													
JJPVAMC (T3 and below, ReWalk)	Group 1			2			4			4			4					14
	Group 2			2			4			4			4					14
	subtotals			4			8			8			8					28
JJPVAMC at KFRC (C5 to T2, Ekso)	Group 1			2			2			2			2					8
	Group 2			2			2			2			2					8
	subtotals			4			4			4			4					16
UMROI (T3 and below, ReWalk)	Group 1			2			3			3			2					10
	Group 2			2			3			3			2					10

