# A Randomized, Crossover Clinical Trial of Exoskeletal-assisted Walking to Improve Mobility, Bowel Function and Cardio-Metabolic Profiles in Persons with SCI

## Statistical Plan and Data Analysis:

The best value achieved for each walking test during sessions 5 to 12 (T1) and from 13 to 36 (T2) will be recorded separately to be used for comparative analysis. These best T1 and T2 scores will be used to determine percent of occurrence with the hypothesized goals. Achievement of the hypothesized goals in the WALK intervention group for the primary outcomes (10mWT, 6minWT and TUG at the 12- and 36-session time points) will be reported as categorical data and presented as a percent of occurrence with the 95% upper and lower confidence intervals (CI). Continuous variables for the Secondary outcomes of the body composition and bowel function variables will be presented as mean  $\pm$ SD. For the continuous variables, a difference score or percent change from pre to post will be calculated for the WALK and UA arms of the study. Comparisons between WALK (Pre-Post) vs. UA (Pre-Post) difference scores will be performed using paired t-tests. Pre to post comparisons for variables that are not normally distributed will be performed by non-parametric tests such as the Wilcoxon signed rank test or the paired sign test.

**Walking outcomes (10mWT, 6minWT, and TUG):** Achievement of the hypothesized goals in the WALK intervention group will be reported as categorical data and presented as percent occurrence with 95% confidence intervals (CI). For each of these outcomes, the best value achieved during the T1 period (sessions 5-12) and the T2 period (sessions 13-36) will be recorded separately and compared to the hypothesized goals, as listed below:

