**Primary Hypothesis (are tested pre and post the WALK arm only):**

1. By session 36, 70% of the participants compared with 10% at session 12 will be able to perform the 10mWT  $\leq$ 40 seconds ( $\geq$ 0.25 m/s);
2. By session 36, 70% of the participants compared with 10% at session 12 will be able to perform the 6minWT distance  $\geq$ 80 m ( $\geq$ 0.22 m/s); and
3. By session 36, 60% of the participants compared with 20% at session 12 will be able to perform the TUGin  $\leq$ 90 seconds.

**Power Calculation:** A one-sample method was chosen to test the observed proportion against the expected proportion determined from the preliminary data of the percent of those who achieved these goals. Using the most stringent criteria above of 20% (session 12) versus 60% (session 36) who achieve the TUG goal, there is 100% power (alpha=5%, double sided Z-power=5.6) with 13 of 63 (20%) versus 38 of 64 (60%) achieving the goal. If the attrition rate is as high as 25%, then the power is still 100%, (alpha=5%, double sided Z-power=4.53), with 10 of 48 (20%) at session 12 versus 29 of 48 (60%) of the participants achieving the goal at session 36.

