## Secondary Hypotheses

1. Bowel function will improve as demonstrated by 25% improvement on the Ten-question bowel survey.
2. Total body fat mass is hypothesized to be reduced by  $2.0 \pm 1.2$  kg

**Power Calculation:** The preliminary data demonstrated a total score change of  $31.5 \pm 7.1$  to  $22.5 \pm 5.3$ , N=8 and a total body fat mass change from  $24.14 \pm 8.45$  to  $22.22 \pm 8.19$ , N=9, alpha=0.05, using a pairwise method, the power for both was 100%. Allowing for 25% dropout, the power is still 100% for 48 participants at an alpha=0.05.

Please note, that both the primary and secondary hypotheses are well powered due to the huge effect observed in the preliminary data. However, performing this study in fewer participants will not permit us to ask many of the exploratory questions. There is no empirical data to support an appropriate power calculation for the exploratory hypotheses.

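### The paired WALK-UA test drops participants who leave in the second arm although their first-arm change is already measured; this modestly widens the secondary-outcome intervals and can bias the contrast if leaving is outcome-related

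*SAP*

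**What the plan says.** The SAP (Statistical Plan and Data Analysis, repeated under the same heading in the protocol) forms a difference score or percent change for each arm, then: "Comparisons between WALK (Pre-Post) vs. UA (Pre-Post) difference scores will be performed using paired t-tests". For variables that are not normally distributed it names "non-parametric tests such as the Wilcoxon signed rank test or the paired sign test". The protocol's Hypotheses section confirms the design of the comparison: "Secondary Hypotheses (are tested between the WALK arm and the UA arm, within-subject".

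On timing, the protocol's Description of Assessments says that DXA "will be performed three times: at baseline, at crossover, and after the second arm of the study". The bowel surveys are given before each intervention and then every two weeks through both arms.

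On attrition, the SAP (Secondary Hypotheses, Power Calculation) says only: "Allowing for 25% dropout, the power is still 100% for 48 participants at an alpha=0.05". Neither document, as supplied, defines an analysis population, an intention-to-treat rule, an imputation method or a mixed model.

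**The concern.** A paired test on WALK minus UA needs both changes from the same person. The crossover assessment closes the first arm, so a participant who leaves during the second 12 weeks already has a full first-arm change in fat mass and bowel score. The planned test cannot use it, and the signed rank and sign tests, if applied to this contrast, have the same limitation.

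Two things are at stake for the secondary outcomes. One is precision: data already paid for do not enter the contrast, and they belong to the randomised comparison made before anyone crosses over. The other is validity: the estimate describes two-arm completers only. A Group 1 leaver goes after receiving WALK and a Group 2 leaver after UA, so if leaving is linked to the first-arm result in one sequence more than in the other, the contrast shifts. The primary walking outcomes are not touched, because they are assessed within the WALK arm.

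**Working it through.** **Inputs from the documents**
- Group sizes: "Group 1 (n=32) will receive exoskeletal-assisted walking (WALK) first for 12 weeks", and the UA-first group is also 32, so 64 in all. With 25% dropout, 64 × 0.75 = 48, the SAP's figure.
- Fat-mass change in the pilot (Preliminary Studies): mean -1.914 kg, SD 1.150 kg, N=9.
- Bowel score in the pilot: 31.5 ± 7.1 to 22.5 ± 5.3, N=8; the SD of the change is not given.
- Two-sided alpha of 5% is stated for the primary outcome ("the power is still 100%, (alpha=5%, double sided Z-power=4.53") and assumed here for the secondary ones.

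**Assumptions, not in the documents**
- ρ, the correlation between a person's two arm changes: -0.5, 0 and 0.5. The crossover value ends one change and starts the other, so measurement error alone pushes ρ towards -0.5.
- How much of the loss falls in the second arm, and how it relates to outcome.
- No period effect (unless stated) and no reversal of Group 1's mean gain during UA.

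**1. The plan's own power.** Fat mass: 1.914/1.150 = 1.664. At N=9, t = 1.664 × √9 = 4.99, P = 0.0011, as the protocol reports. At n=48 the noncentrality is 1.664 × √48 = 11.5, power over 99.99%. Bowel: a 9.0-point change, with pre-post correlation assumed from 0 to 0.8 (SD of change 8.86 to 4.28), gives over 99.9% at n=48. The stated 100% therefore reproduces, though for a one-arm change. For the WALK-UA contrast the SD is 1.15 × √(2(1-ρ)) = 1.99, 1.63 or 1.15 kg, and power at 48 is still over 99.9%. For bowel, with an assumed SD of change of 7.1 and an effect of 25% of 31.5 = 7.9 points, it is at least 99.1%.

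**2. Precision.** Let N1 have a first-arm change and m have both, balanced by sequence, with leaving unrelated to outcome.
- Complete pairs: SE = SD × √(2(1-ρ)/m).
- Likelihood model with intervention and period, keeping first-arm-only participants: SE = SD / √(N1/4 + (m/4)(1+ρ)/(1-ρ)).
- Ratio = √((1-ρ)/2 × N1/m + (1+ρ)/2).

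| ρ | Pairs SE, N1=64, m=48 (kg) | Model SE (kg) | Ratio | Ratio if only 8 leave, all in arm 2 (m=56) | Ratio if the 25% is spread evenly (N1=55.4, m=48) |
|---|---|---|---|---|---|
| -0.5 | 0.288 | 0.257 | 1.118 | 1.052 | 1.056 |
| 0 | 0.235 | 0.217 | 1.080 | 1.035 | 1.038 |
| 0.5 | 0.166 | 0.160 | 1.041 | 1.018 | 1.019 |

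Even spread means 64 × √0.75 = 55.4 finishing the first arm, so about 7 first-arm changes go unused. The ratio does not involve the SD, so it applies to bowel as well. Nor does it depend on total N, so the conflict between 64 and the 132 stated elsewhere in the protocol does not affect it (that conflict needs its own reconciliation).

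**3. Bias if poor WALK responders in Group 1 leave.** Suppose a Group 1 member leaves during UA with probability 0.8 if the WALK change was worse than average and 0.2 otherwise, and nobody in Group 2 leaves. Sixteen of 32 stay, 16 of 48 pairs. Stayers' mean WALK change is shifted by -0.6 × 0.798 × 1.15 = -0.55 kg (0.798 = √(2/π)), and their UA change by ρ times that. Bias = -0.55 × (1-ρ) × 16/48 = -0.28, -0.18, -0.09 kg for ρ = -0.5, 0, 0.5. Simulation of 3,000 trials per case gave 0.27, 0.18 and 0.09 kg overstatement (14%, 10%, 5% of 1.914); the likelihood model's bias was under 0.01 kg.

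**4. Other leaving patterns.** Random leaving at 25%: no bias. Leaving that depends on the first-arm result equally in both sequences: the shift is (1-ρ)s in Group 1 and -(1-ρ)s in Group 2, which cancel. Poor responders in Group 2 leaving during WALK: complete pairs overstate by 0.27, 0.18 and 0.09 kg, and the likelihood model still overstates by 0.16, 0.23 and 0.19 kg.

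**The case against.** The case for leaving the plan alone has four parts.

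*No outcome-related leaving is documented.* This stands. The protocol reports "In 13 participants enrolled to date at the JJPVAMC, three withdrew", for a job move, an unrelated illness and travel. Its remark that people would be reluctant to join a trial that might deny them walking is about enrolment. A reader might infer that Group 1 members who gained little will leave once walking is over, and so that the paired test is biased. That is a conjecture.

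*The loss may be small.* A reader might apply 3/13 to each arm: 64 × 10/13 = 49 finish the first and 49.2 × 10/13 = 38 finish both, so about 11 measured changes are discarded. The documents do not support this. It implies 41% loss against the plan's 25%, and the rate appears to come from the single-group walking pilot, not from a UA arm with phone calls and twice-monthly visits.

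*Nothing would change.* Largely true for significance: power is near 100% and these are secondary outcomes. Nor are first-arm data lost to all reporting, since the SAP also presents means and changes by arm. What remains is the estimate and interval for the WALK-UA contrast.

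*A mixed model has weaknesses of its own.* Two hold. It does not repair outcome-related loss during Group 2's WALK arm, and at ρ of 0 and 0.5 it was further off there than complete pairs. And a random participant effect alone cannot represent a negative correlation, which the protocol's hypothesis that Group 1's fat loss reverses during UA could produce. In a simulation with ρ = -0.5 and 25% random dropout, such a model reported an SE of 0.226 kg against a true 0.281 kg, with 88% coverage; the paired test had 94%. Both points shape the fix; neither favours discarding measured data.

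**Conclusion.** The point holds in a limited form. That second-arm leavers are excluded from the WALK-UA contrast follows directly from the choice of test. The cost in precision is 4 to 12% on the interval if all 25% attrition falls in the second arm, and about 2 to 6% if it is spread evenly, for ρ between -0.5 and 0.5.

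Bias is possible, not established: 0.1 to 0.3 kg of a 1.9 kg effect under strong assumed selection, and zero if leaving is random at the same rate in both sequences. If leaving is random but unequal by sequence, the planned test, having no period term, also picks up part of any period effect. With an assumed 0.5 kg period effect and 46% of Group 1 but none of Group 2 leaving (17 and 32 pairs), the shift is about 0.5 × (32-17)/49 = 0.15 kg. The sizes rest on the pilot SD of 1.15 kg and on no reversal during UA. Reversal would alter what either analysis estimates and is a separate question.

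The change is worth making because it is cheap and bears on both secondary outcomes. It is not a threat to the primary outcomes or to power.

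**What to change.** In the Statistical Plan and Data Analysis section of both the SAP and the protocol:

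1. Make the main secondary analysis a likelihood-based repeated-measures model of each arm's change, with fixed effects for intervention and period and an unstructured within-participant covariance, not only a random participant effect.
2. Define the analysis population as every randomised participant with at least one completed arm.
3. Keep the paired t-test on two-arm completers as a sensitivity analysis.
4. Report second-arm leaving by sequence, with reasons.
5. Add a not-at-random sensitivity analysis, for example shifting the unobserved WALK changes of Group 2 leavers over a stated range.

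The cost is SAP and protocol wording and slightly more analysis work; no new visits or measurements. The model assumes that leaving is explained by observed data (missing at random), which is why item 5 is needed. Participants who leave during the first arm still have no completed change and are not recovered by this.

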**Primary Hypothesis (are tested pre and post the WALK arm only):**

1. By session 36, 70% of the participants compared with 10% at session 12 will be able to perform the 10mWT  $\leq$ 40 seconds ( $\geq$ 0.25 m/s);
2. By session 36, 70% of the participants compared with 10% at session 12 will be able to perform the 6minWT distance  $\geq$ 80 m ( $\geq$ 0.22 m/s); and
3. By session 36, 60% of the participants compared with 20% at session 12 will be able to perform the TUGin  $\leq$ 90 seconds.

**Power Calculation:** A one-sample method was chosen to test the observed proportion against the expected proportion determined from the preliminary data of the percent of those who achieved these goals. Using the most stringent criteria above of 20% (session 12) versus 60% (session 36) who achieve the TUG goal, there is 100% power (alpha=5%, double sided Z-power=5.6) with 13 of 63 (20%) versus 38 of 64 (60%) achieving the goal. If the attrition rate is as high as 25%, then the power is still 100%, (alpha=5%, double sided Z-power=4.53), with 10 of 48 (20%) at session 12 versus 29 of 48 (60%) of the participants achieving the goal at session 36.

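### The primary hypotheses compare sessions 13-36 with sessions 5-12 in the same participants, but the only test tied to them is one-sample, and the stated 100% power is not power to show improvement.

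*SAP*

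**What the plan says.** The SAP heading for the primary hypotheses says that they "are tested pre and post the WALK arm only". Each one is a contrast over time: 10% to 70% for the 10-metre and 6-minute walks, and 20% to 60% for the TUG. The data come from two windows: "The best value achieved for each walking test during sessions 5 to 12 (T1) and from 13 to 36 (T2) will be recorded separately".

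For analysis, the SAP's Statistical Plan says that goal attainment "will be reported as categorical data and presented as a percent of occurrence with the 95% upper and lower confidence intervals (CI"). The two sets of scores are also to be compared with the hypothesised goals. No test of T2 against T1 is named for these outcomes.

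A test appears only under Power Calculation: "A one-sample method was chosen to test the observed proportion against the expected proportion determined from the preliminary data". The main claim there is that "there is 100% power (alpha=5%, double sided Z-power=5.6) with 13 of 63 (20%) versus 38 of 64 (60%) achieving the goal". The 25% attrition case gives "double sided Z-power=4.53), with 10 of 48 (20%) at session 12 versus 29 of 48 (60"%). The Protocol's statistical section repeats this text.

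Paired methods are mentioned once. After the continuous secondary outcomes, the SAP says that pre-to-post comparisons of non-normal variables "will be performed by non-parametric tests such as the Wilcoxon signed rank test or the paired sign test".

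Protocol Primary Hypothesis 2 says that "70% of the participants compared with 10% at session 12 will be able to perform the 6min WT distance" of 80 m or more. Protocol Primary Aim 1.b.ii gives 20%, not 10%, for the same distance at the same session.

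**The concern.** A one-sample test compares one observed share with a fixed number. It cannot say whether the same people did better at T2 than at T1, because T1 does not enter it. If the power paragraph describes the intended test, test and hypothesis do not match. If it does not, the hypotheses have no assigned test.

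At stake is the main conclusion. Two percentages with separate intervals do not amount to a paired inference, and no rule is given for turning them into a statement about improvement. A reader would also take the 100% as power for the hypothesis printed directly above it.

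**Working it through.** **Inputs.** SAP, Power Calculation: TUG 20% at session 12 and 60% at session 36, two-sided alpha 5%, n = 64, and 48 after 25% attrition. The documents give no T1-T2 correlation, so I take the full possible range.

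**1. The plan's own figure.** One-sample normal approximation, null p0 and true rate p1:

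Z-power = (|p1 − p0|·√n − 1.96·√(p0(1−p0))) / √(p1(1−p1))

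- Null 0.60, truth 0.20, n = 64: (0.40×8 − 1.96×0.4899)/0.40 = (3.200 − 0.960)/0.40 = 5.600. Printed: 5.6.
- Same, n = 48: (0.40×6.928 − 0.960)/0.40 = 4.528. Printed: 4.53.
- Null 0.20, truth 0.60: (3.200 − 1.96×0.40)/0.4899 = 4.93 for n = 64, and 4.06 for n = 48. No match.
- Two-sample pooled formula: 2.91 for 64 against 64, and 2.24 for 48 against 48. No match.

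Using n = 63, the observed counts, a continuity correction or an arcsine form did not match both values either. The printed power is thus the chance of rejecting 60% when the true rate is 20%, a rejection in the downward direction. Against a 60% null, the plan's hoped-for results of 38/64 and 29/48 each give an exact p of 1.0, and an upward rejection would need 47/64 (73%).

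**2. Power for the hypothesis as written.** Let b be the probability of reaching the goal at T2 but not at T1, and c the reverse, so b − c = 0.60 − 0.20 = 0.40. The exact McNemar test takes the D participants whose status changed and rejects if twice the upper binomial(D, ½) tail is 0.05 or less. Power sums this over D ~ binomial(n, b + c).

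| TUG, 20% to 60% | b | c | n = 64 | n = 48 |
|---|---|---|---|---|
| Nobody loses the goal | 0.40 | 0 | >99.9% | >99.9% |
| T1 and T2 independent (c = 0.20×0.40) | 0.48 | 0.08 | 99.6% | 97.3% |
| Every T1 achiever loses it | 0.60 | 0.20 | 95.2% | 86.8% |

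For 10% to 70%, power is at least 99.9% at both sizes in every case. If the 80 m goal starts from the Aim's 20% (20% to 70%), it is at least 99.2% and 96.4%.

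**3. A hypothetical.** Suppose T2 alone were tested against 20% and T1 set aside. The exact upward cut-off is 20/64 or 16/48. A rate of 30% at both sessions would then be declared above 20% in 46% (n = 64) or 36% (n = 48) of trials, and a flat 40% in 94% or 86%. For the 80 m goal with null 10%, a flat 20% gives 65% or 50%.

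**4. Unequal windows.** T1 is the best of up to 8 sessions (5 to 12) and T2 the best of up to 24 (13 to 36). Assume a latent-normal score, flat ability, T1 = 20%, n = 64 and a test at every session. McNemar on the two bests would then declare improvement in about 60% of trials if the correlation between a person's sessions is 0.5, and in about 4% if it is 0.95. With weekly testing (best of 3 against best of 8), the rates are about 57% and 5%. With equal windows the rate is 1.5% or less. The documents give no such correlation, so this shows direction and a range only.

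**The case against.** - **The one-sample sentence appears only under power.** The analysis text never says that T2 will be tested alone, and it reports both T1 and T2, so a flat result would be visible. This stands. A reader might infer from step 3 that the plan would falsely claim improvement 46% to 94% of the time. The documents do not support that. Those rates describe an analysis that the plan never explicitly adopts, and the pilot text says that all ten participants improved.
- **Many primary aims are fixed targets,** and a proportion with a CI against a target suits them. For those aims, p = 1.0 at 38/64 simply means agreement with the target. This stands for the aims. It does not cover the hypotheses, which add the T1-T2 contrast.
- **A paired route is partly there.** On yes/no data the paired sign test is the exact McNemar test, and the heading speaks of pre and post. But the sentence follows the continuous secondary outcomes, and nothing assigns it to the walking goals. It may be what was meant; the plan should say so.
- **The power error has little consequence.** Reversing the null still gives about 100%, and the 95% and 87% cases are implausible for a best-of-many score in people still training. The 60% null is inferred from matching the arithmetic and may reflect only the order of entry. All of this is fair. The printed figure still answers another question.
- **The hypotheses define a cumulative best by session 36.** This stands, and it is why the equal-window contrast belongs in a sensitivity analysis.

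**Conclusion.** The plan assigns no test to the comparison that its primary hypotheses make, and its 100% power figure belongs to a different, one-sample question. That rests on the SAP text and on both Z-powers being reproduced to rounding. The null of 60% is an inference from that match.

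A reader might conclude that the trial is too small. It is not, under the plan's own rates: paired power for the TUG runs from 95.2% to above 99.9% with 64 and from 86.8% to above 99.9% with 48, and it is higher for the two walks. The 10%/20% conflict changes a stated goal and leaves the adequacy of the sample size intact. These powers assume that the planned T1 and T2 rates are true and that each counted participant has both scores.

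This should be fixed before analysis. It is a matter of specification, and the data to be collected are sufficient.

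**What to change.** 1. State that, for each primary hypothesis, T1 and T2 goal status will be compared within participant by an exact two-sided McNemar test, with a 95% CI for the paired difference. If the paired sign test was meant to cover the walking goals, say so. Keep the percentages with CIs for the fixed-target aims.
2. Replace the power sentence: for 20% to 60%, power is about 99.6% (n = 64) and 97.3% (n = 48) if T1 and T2 status are independent, near 100% if nobody loses the goal, and 95% and 87% in the extreme case where every T1 achiever loses it.
3. Reconcile 10% with 20% for the 80 m goal at session 12, and 63 with 64 in the power text. A paired test has one denominator.
4. Report the same McNemar contrast with equal windows, for example sessions 29-36 against 5-12, as a sensitivity analysis beside the main result. It should not be a condition of the primary conclusion.

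The cost is SAP wording, a slightly lower stated power and one extra analysis of data already collected. The equal-window result may be less favourable.
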